COMIRB Protocol

COLORADO MULTIPLE INSTITUTIONAL REVIEW BOARD
[name] [contact] [contact]

Protocol #: 21-2886

Project Title: Opioid Modulation and Neural Reward Activation in Healthy Adults

Principal Investigator: [name]

Version Date: 10/28/21

I. Hypotheses and Specific Aims:

1. Evaluate whether mu-opioid receptor blockade via naltrexone alters reward activation in the ventral striatum. In a study of 10 healthy, moderate drinking adults, we will use a crossover design to examine brain activation during a functional MRI scan during placebo and mu-opioid blockade.

Hypothesis 1. Relative to the placebo scan, participants will show reduced reward-related activation in the ventral striatum during the active medication scan.

2. Evaluate whether mu-opioid receptor blockade alters threat activation in the amygdala. In the same sample and design from Aim 1, we will use the Emotion Regulation Task to assess threat related activation in the amygdala during a functional MRI scan.

Hypothesis 2. Opioid receptor modulation will not affect threat related activation, consistent with naltrexone primarily targeting reward motivation.

3. Examine whether mu-opioid receptor blockade via naltrexone alters valuation of alcohol. In the same sample and study design from Aim 1, we will use the Alcohol Purchase Task to assess subjective value of an alcoholic beverage in order to link opioid-modulation directly to alcohol motivation.

Hypothesis 3. Relative to the placebo session, participants will be willing to pay less money for an alcoholic beverage during the active medication session.

This proposal aims to fill a gap in understanding how endogenous opioid function affects reward response in the brain. One of the leading hypotheses is that individuals who drink to maximize reward are more likely to benefit from naltrexone treatment, and the current proposal would provide evidence for this in a healthy sample. Further, this work could lead to a clinical study of reward-related brain activation and response to naltrexone treatment in adults with an Alcohol Use Disorder. This stands to improve precision medicine approaches to tailor treatments for alcohol use disorder.

II. Background and Significance:

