Our goal is to better understand the neurobiology of reward processing by probing other neurotransmitter systems that interact with dopamine to regulate reward. The objective of this application is to establish whether healthy adults show reduced reward-related activation in the nucleus accumbens when ramped up to steady state dosing with naltrexone. Naltrexone is a mu-opioid antagonist and one of three medications approved by the Food and Drug Administration for the treatment of alcohol use disorder. We will also examine threat processing as a control paradigm to establish that opioid modulation primarily affects reward processing. Since diminishing reward signaling may reduce incentive to seek alcohol, we will also examine a measure of subjective alcohol evaluation. We are prepared to conduct this study based on our expertise in psychopharmacology and functional MRI studies of reward and threat processing as well as psychiatric disorders. This qualified group of investigators will make certain that our research adheres to both neuroscientific theory of reward processing as well as clinical application.

III. Preliminary Studies/Progress Report:

In a currently ongoing study, we have recruited 45 adults to complete the monetary incentive delay task and we have shown a strong main effect of cue type in nucleus accumbens activation ($F_{2,210} = 58.8, p < 0.001$), where activation is greatest during cues to gain \$5 (Figure 1).

[figure not shown]
[figure not shown]

Figure 1. Using the monetary incentive delay task, we found a main effect of cue on nucleus accumbens activation ($F_{2,210} = 58.8$, $p < 0.001$).

IV. Research Methods

A. Outcome Measure(s): There are three outcomes for this study: nucleus accumbens activation to monetary reward, amygdala activation to threat, and subjective alcohol evaluation. For nucleus accumbens activation, we will use percent signal change in response to the cue to earn \$5 during the Monetary Incentive Delay task. For the amygdala response to threat, we will use the percent signal change in response to negative images in the Emotion Regulation task. For the valuation of alcohol, we will use the Alcohol Purchase Task to assess the greatest expenditure on drinks (price paid multiplied by number of drinks).

B. Description of Population to be Enrolled:

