- i. **Alcohol Purchase task (APT)**: (Kaplan et al. 2018): After the scan, we will administer this task to determine the amount individuals are willing to pay for alcohol. In the alcohol purchase task, participants first read the following vignette: "Imagine that you and your friends are at a bar from 9 p.m. to 2 a.m. to see a band. The following questions ask how many drinks you would purchase at various prices. The available drinks are standard size beer (12 oz.), wine (5 oz.), shots of hard liquor (1.5 oz.), or mixed drinks with one shot of liquor. Assume that you did not drink alcohol before you went to the bar and will not go out after." Participants will then be asked "How many drinks would you consume if they were _____ each?" 14 costs will be listed: \$0 (free), \$0.25, \$0.50, \$1.00, \$1.50, \$2.00, \$2.50, \$3.00, \$4.00, \$5.00, \$6.00, \$7.00, \$8.00, and \$9.00.
- ii. **Iowa gambling task**: (IGT) is a psychological task thought to simulate real-life decision making. It was introduced by Antoine Bechara, Antonio Damasio, Hanna Damasio and Steven Anderson, then researchers at the University of Iowa (Bechara et al. 1994). We will use the often computer based version of the task. The task was originally developed to detect problems patients with damage to the ventromedial prefrontal cortex. This part of the brain is, among other things, involved in processing risk, fear, emotion, and decision making.
- iii. **Delay-Discounting Task**: (DD) is a measure of temporal discounting, the tendency for people to prefer smaller, immediate monetary rewards over larger, delayed rewards. Participants complete a series of 5 questions that each require choosing between a smaller, immediate reward (e.g., \$500 today) versus a larger, later reward (e.g., \$1000 in 25 days). The 5 items are divided into three groups according to the size of the larger amount (small, medium, or large) (Koffarnus and Bickel 2014). Modeling techniques are used to fit the function that relates time to discounting. The main dependent measure of interest is the steepness of the discounting

curve such that a more steeply declining curve represents a tendency to devalue rewards as they become more temporally remote.

D. Description, Risks and Justification of Procedures and Data Collection Tools:

a. Justification for Exclusion of Vulnerable Populations:

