E. Potential Scientific Problems: One challenge of our study is that we will not directly observe naltrexone binding. Directly observing naltrexone's activity would require PET imaging to observe displacement of a tracer that binds to opioid receptors, but we will not do that in this study due to cost and time. Thus, even if we observe behavioral or neural effects, we will not know if naltrexone is acting at that site. However, since we are using a randomized, placebo-controlled design, we can still draw conclusions about naltrexone causing the changes even if the changes may be downstream from naltrexone's direct site of action.

F. Data Analysis Plan: Outcomes will be examined using paired t-tests for two times (active medication, placebo). Functional MRI analysis will be conducted with AFNI software (Cox 1996). Functional images will be time-slice corrected and co-registered with anatomical images. Anatomical images will be non-linearly warped to standard space and an identical transformation will be applied to the functional image. Functional images will be blurred using a 4mm Gaussian kernel and values will be scaled to have a mean intensity of 100. A regression algorithm will be applied including six regressors to account for motion. For the monetary incentive delay task, regressors of interest include the gain, loss, and neutral cue. For the emotion regulation task, regressors of interest include neutral, look, and decrease conditions. For the monetary incentive delay task, activation will be extracted from the nucleus accumbens for each of the three cues. For the emotion regulation task, activation will be extracted from the amygdala for each of the three conditions. As an exploratory analysis, we will conduct whole-brain, voxel-wise analysis.

Sample Size and Power Considerations. In terms of evaluating differences in reward activation between placebo and mu-opioid antagonism conditions, a study of mice estimated a large effect size of mu-opioid antagonism on reward response in the nucleus accumbens, with Cohen's $d > 1.0$ (Walters et al. 2005). A study of kappa-opioid receptor modulation in human reward response measured with functional MRI found a medium to large effect size of Cohen's $d = 0.6$ (Krystal et al. 2020). We specified significance level alpha=.05, two-tailed, and power of 0.8. A sample of 9 adults would provide 80% power to detect an effect size of 1.0 or greater as significant.

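### The H3 outcome is peak spending on a price list that ends at $9, so it understates a fall in anyone whose spending is still rising there; H3 is worded as a price, but the measure combines price and quantity

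*Combined protocol and SAP*

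**What the plan says.** Section I, Aim 3, will use the Alcohol Purchase Task to "assess subjective value of an alcoholic beverage". Hypothesis 3 is that, compared with placebo, "participants will be willing to pay less money for an alcoholic beverage during the active medication session".

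Section IV.A defines the outcome: the task will be used to "assess the greatest expenditure on drinks (price paid multiplied by number of drinks").

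Section IV.C.e.i describes the task as a way "to determine the amount individuals are willing to pay for alcohol". Participants answer "How many drinks would you consume if they were" a given price each, and "14 costs will be listed", running from free to $9.00 in $1 steps from $3 upward.

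Section IV.F gives the analysis: "Outcomes will be examined using paired t-tests for two times (active medication, placebo").

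The documents name no other demand index and give no rule for a participant who is still buying, or still spending more, at $9. They give no expected mean, SD or power for this outcome.

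**The concern.** Two separate features are involved.

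- **The end of the list.** Greatest expenditure is a maximum over the prices asked. If spending would go on rising past $9, the recorded value is spending at $9, not the true peak. This affects the participants who value alcohol most highly.
- **Claim and measure.** H3 speaks of paying less for a beverage, which most readers will take as a price. Peak expenditure is price times quantity and can move, or stay still, for reasons that a single price does not describe.

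At stake is how large an effect Aim 3 can report, and whether its conclusion can be stated in H3's words. Section IV.G says the pilot data are to support a further grant application, so the size of the estimate matters as well as its p-value.

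**Working it through.** **The plan's own figure.** There is none for this outcome. The sample-size paragraph ("We specified significance level alpha=.05, two-tailed, and power of 0.8") concerns reward activation and does not bear on this point.

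**1. Effect of the $9 limit.** The 14 prices are from IV.C.e.i. The demand curve is an assumption.

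- Drinks at price P: Q = 6·exp(−bP).
- Spending P·Q peaks at P = 1/b, with value 6/(b·e).
- Raising b by 25% lowers the true peak by 1 − 1/1.25 = 20%, whatever b is.
- When both sessions peak above $9, the list maximum is at $9, namely 9 × 6·exp(−9b) = 54·exp(−9b). The fall the list shows is then 1 − exp(−2.25b). For a placebo peak at $12, b = 1/12 and the fall is 1 − exp(−0.1875) = 17.1%.

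Dollar falls below are taken before rounding.

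| Placebo peak price | List value, placebo | List value, naltrexone | Fall on list | Fall on list, % | True fall (20%) | List % ÷ 20% |
|---|---|---|---|---|---|---|
| $6 | $13.24 | $10.59 | $2.66 | 20% | $2.65 | 1.00 |
| $9 | $19.87 | $15.89 | $3.98 | 20% | $3.97 | 1.00 |
| $12 | $25.51 | $21.15 | $4.36 | 17% | $5.30 | 0.85 |
| $15 | $29.64 | $25.51 | $4.13 | 14% | $6.62 | 0.70 |
| $18 | $32.75 | $28.90 | $3.85 | 12% | $7.95 | 0.59 |
| $27 | $38.69 | $35.60 | $3.09 | 8% | $11.92 | 0.40 |

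With demand 1.5 times steeper, the true fall is 33%. The list shows 33% for a placebo peak at or below $9, 30% at $12.50 and 20% at $20.

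The limiting case is a participant who buys 4 drinks at every price from $5 to $9 in both sessions. The score is 4 × $9 = $36 each time, and a change that begins above $9 gives a difference of exactly zero.

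**2. Price and quantity.** Drink counts here are invented for illustration.

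- Placebo: 5 drinks at $4, 4 at $5, 3 at $6, 2 at each of $7 to $9. Naltrexone: the same up to $6, then none. Peak expenditure is 5 × $4 = 4 × $5 = $20 in both sessions, although the highest price at which anything is bought falls from at least $9 to $6.
- 4 drinks at $9 becoming 2 at $9, with $9 still the peak, takes the outcome from $36 to $18, although both sessions still buy at the top price.

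The first pattern lies inside the list, so a longer list alone would not make the outcome a measure of price.

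**3. Does shrinkage mean lost power?** The paired t-test depends on the mean dollar difference divided by its SD, and the limit compresses both. The documents give neither, so every run here rests on assumed variation.

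- With exponential curves, lognormal placebo peaks (log-SD 0.3 or 0.6) and session noise only in b (log-SD 0.15 or 0.3), the standardised effect at a median peak of $9 is 0.50 to 1.03 on the list, against 0.41 to 0.95 unrestricted. At a median of $18 it is 0.51 to 1.04 against 0.41 to 0.95.
- With answers in whole drinks and quantity also varying between sessions, the order reverses: 0.43 on the list against 0.69 on an extended list at a median peak of $18, 0.61 against 0.71 at $9, and roughly equal at $6.

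The direction therefore depends on inputs that the plan does not supply.

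**The case against.** The strongest reply is that the limit does not make high-value drinkers uninformative. In the table, participants peaking at $12 to $27 still contribute falls of $3.09 to $4.36, more than the $2.66 of someone peaking at $6, and the t-test works on dollars. This stands. A reader might infer that the list biases H3 toward no effect, or that the 15% to 60% is lost power. The documents support neither. One can compute that power at 10 participants drops from about 80% to 65% or 55% if 20% or 30% of them score exactly zero and the rest have a standardised effect of 1.0. But exact zeros need unchanged purchases at every listed price that could set the peak, and nothing in the documents suggests how often that happens. The sample is described as healthy, moderate drinkers; a $27 peak implies 6·exp(−9/27) = 4.3 drinks at $9 and about $60 of peak spending.

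The reply goes too far if it claims that the limit never hurts: the whole-drink runs above show that it can.

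On wording, paying less money can be read as total spending, and the outcome is clearly prespecified. A reader might also infer that a positive result would say nothing about willingness to pay. That is too strong. Someone who goes from 6 drinks at $5 to 4 at $5 no longer finds the fifth and sixth drinks worth $5, which is a lower valuation of alcohol. What remains is that the phrase about a beverage and the measure do not match.

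**Conclusion.** The point holds in a limited form. For a participant whose spending is still rising at $9, the list sets the outcome, and a fall caused by steeper demand is understated. Under the assumed curve and a 25% change, 15% to 60% of the percentage fall is missed for placebo peaks between $12 and $27, and essentially none for peaks at or below $9. A proportional drop in drinks at every price would keep its full percentage on either list. If drinks fall or stay equal at every listed price, the outcome cannot rise, so under that condition the risk is a diluted, null or mislabelled effect and not a reversed one.

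The share of participants above $9 is unknown, so the overall effect on the H3 estimate cannot be computed. Loss of power and bias toward no effect are possible but not shown. The wording mismatch is real, needs no assumption about the limit, and is cured by a sentence. This is a cheap improvement worth making before data collection, because prices that were not asked cannot be recovered afterwards.

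**What to change.** Before data collection:

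1. Add a fixed set of prices above $9 after the existing 14, identical for everyone and in both sessions. The 14-price value can then still be computed. A list that continues until the individual stops buying should be avoided, since its length could differ between one person's two sessions.
2. Keep greatest expenditure as the single H3 outcome, which avoids a second test at this sample size, and reword H3 as lower peak expenditure on alcohol in the naltrexone session than in the placebo session.
3. Report the highest price with any purchase only as a secondary measure, on the extended list. On the $9 list it would be heavily censored; in assumed runs its standardised effect there was only 0.01 to 0.46.
4. Report how many participants have their greatest expenditure at $9 on the 14 prices, and how many at the last price of the extended list.

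Cost: a few more items in a short questionnaire, two edited sentences, and a dollar outcome that will be somewhat more variable.

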- a. **Recruitment, sample description and inclusion/exclusion criteria.** Participants will be recruited through advertisements on social media, paper flyering, advertising on local list-servs, and by peer recruitment. Our lab has successfully attracted over 340 participants to complete our screening measures using these methods in the past year. Interested individuals can contact the laboratory via email or phone call to arrange a phone screen, where we will assess likely eligibility for the study.
 - i. **Inclusion criteria:** A) Between 18 and 35 years of age,
 - ii. **Exclusion criteria:** A) AUDIT Score less than or equal to 14, B) Non-drinker C) positive result on urine drug screen or breathalyzer at the start of any study visit, D) inability to complete MRI (e.g. presence of ferromagnetic objects in body), E) current use of medications that alter the hemodynamic response, such as insulin, F) history of trauma resulting in loss of consciousness longer than 15 minutes, G) for females, pregnancy, H) current (within the last 3 months) use of opioids to avoid acute precipitated withdrawal due to opioid receptor antagonism I) treatment for a DSM5 disorder other than anxiety or depression through therapy J) treatment for a DSM5 disorder through medications, K) greater than 10 uses of illicit substances in the last year.
- b. **Feasibility:** We have recruited 45 participants to our laboratory's studies in the past year and conducted 45 MRI scans. To recruit ~10 participants in one year, we need to recruit 1 participant per month and conduct 2 scans per month. This is well within the capacity of our laboratory operations.

C. Study Design and Research Methods. After completing an informed consent procedure, participants will sign a consent form. They will then complete a psychiatric interview and receive 5 capsules. Participants will return five days later for visit 2. On visit 2, they will complete a medication side-effect questionnaire. If they report side effects that are more

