than mild (i.e. if they report moderate or severe side effects), a medical professional (i.e. nurse or physician) will follow up to confirm that they are ok to complete the MRI and provide care as needed. All participants will complete a breathalyzer and saliva drug test to confirm sobriety. Females will be asked to provide a urine sample for a pregnancy test. Participants will then complete an MRI and the Alcohol Purchase Task. They will be sent home with 5 days' worth of capsules. They will return after 5 days and repeat the same procedures.

- a. Dosing. We will administer doses of naltrexone and placebo. Dosing will be double-blind and counter balanced. Participants will receive 5 capsules on their first visit to take during the week. They will receive 5 additional capsules to take each day of the following week. Naltrexone will be over-encapsulated by the Investigational Drug Service at the School of Pharmacy. Matching placebo capsules will contain methylcellulose powder. Naltrexone will be taken once daily by mouth and ramped up by the following schedule: Monday-25mg, Tuesday-25mg, Wednesday-50mg, Thursday-50mg, Friday-50mg. A study coordinator blind to the contents of the capsules will deliver the capsules to the participant. The Investigational Drug Service will maintain blinding and will track dosage, to be revealed following study completion. Half of participants will receive placebo during week 1 and half will receive placebo during week 2. Remote video monitoring will also be used to assess adherence. Participants will receive a text message on their mobile phones at 9 am each morning reminding them to take the medication and instructing them to upload a video of themselves doing so to a secure data repository (REDCap). A study-provided mobile phone will be available for participants who do not own a mobile phone or who are not willing to use their phone for this purpose (i.e., due to concerns about mobile data cost). The digital timestamps of these videos will subsequently be extracted, and their contents reviewed, to verify that the participant ingested the medication at the instructed time. Other studies of non-treatment-seeking individuals have reported success with remote video monitoring (DeWorsop et al. 2016).

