Liver damage or hepatitis is possible. Patients should tell their practitioner about any of the following symptoms during treatment: stomach area pain lasting more than a few days, dark urine, yellowing of the whites of your eyes, tiredness, Practitioners may need to stop treatment using naltrexone if patients develop signs or symptoms of a serious liver problem, Depressed mood, Pneumonia, Serious allergic reactions, Skin rash, swelling of face, eyes, mouth, or tongue, trouble breathing or wheezing, chest pain, feeling dizzy or faint.

iii. Minimizing risk

Remote video monitoring will also be used to assess adherence. Dosing size will be set before participants receiving the naltrexone and participants will start on smaller doses (25mg) for two days before being raised to the final dosing to allow for adjustment to naltrexone and in case of adverse reaction to naltrexone. We will use a questionnaire to check for adverse reactions and will provide care as needed for moderate or severe side effects, such as nausea.

e. Psychological Tests

i. During the Standardized Clinical Interview for the DSM-V (SCID)
participants may discuss negative or traumatic events they have experienced. The SCID will be administered by a trained psychiatrist or by a member of the team trained by the team psychiatrist. Some of the questionnaires may cause emotional distress by asking about traumatic or unpleasant events from a person's life. While most individuals will tolerate this discomfort without problems, it is possible that the memories may trigger unhappiness. To mitigate the risk, study staff will allow participants to take breaks as needed. If serious distress arises, participants will be referred to a psychiatrist from the study team. This protocol may identify mental health problems, such as depression, suicidality, or substance use disorders. Problems with acute danger, such as suicidality will receive immediate attention and intervention. Individuals with diagnoses such as depression or alcohol use disorder will be given referrals for treatment.

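### No side-effect check is scheduled between the two 25 mg days and the step to 50 mg

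*Combined protocol and SAP*

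**What the plan says.** Section IV.C.a (Dosing) fixes the naltrexone schedule as "Monday-25mg, Tuesday-25mg, Wednesday-50mg, Thursday-50mg, Friday-50mg". The capsules for a week are given out together: "Participants will receive 5 capsules on their first visit to take during the week", with a second set of five for the following week. The order is counterbalanced: "Half of participants will receive placebo during week 1 and half will receive placebo during week 2".

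Section IV.D.d.iii (Minimizing risk) gives two reasons for the low-dose days. Participants stay at 25 mg "for two days before being raised to the final dosing to allow for adjustment to naltrexone and in case of adverse reaction to naltrexone". The next sentence adds "We will use a questionnaire to check for adverse reactions and will provide care as needed" for moderate or severe effects, but names no day.

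Section IV.C (Study Design and Research Methods) supplies the only dates. Visit 2 is five days after the first handout, and "On visit 2, they will complete a medication side-effect questionnaire". For the second week, "They will return after 5 days and repeat the same procedures". If effects are more than mild, a nurse or physician confirms fitness for the MRI and gives care as needed.

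Between visits, the one planned contact is in IV.C.a: "Participants will receive a text message on their mobile phones at 9 am each morning reminding them to take the medication", with a video upload. Its stated use is adherence, and no symptom question is described.

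**The concern.** The two 25 mg days are justified partly as a precaution against adverse reactions. For a reaction on those days to change what happens next, someone has to know of it before the dosing day 3 capsule. A participant may volunteer the information or leave the capsule untaken. If neither happens, no dated procedure in the documents would bring the reaction to light until the return visit.

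What is at stake is participant safety. These are healthy volunteers, and section IV.D.b states that they gain no known direct benefit. Someone with a moderate or severe reaction at 25 mg who stays silent and keeps to the schedule would take two or three capsules of twice that strength before anyone is due to ask.

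**Working it through.** The plan states no figure for this point. The check sets the dose schedule against the dated contacts.

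**Inputs**
- Doses on days 1 to 5: 25, 25, 50, 50, 50 mg (IV.C.a).
- All five capsules are handed out at the start of each week (IV.C, IV.C.a).
- The questionnaire is at the return visit, five days after handout, in both weeks (IV.C).
- About 10 participants recruited over one year (IV.B.b), each with two weeks of capsules.

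The documents do not say whether the first capsule is taken on the day of handout, so two cases bound the answer.

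**Case A: first capsule on the handout day.** Handout and capsule 1 on Monday, return on Saturday.
- Taken by the check: 5 capsules, 25 + 25 + 50 + 50 + 50 = 200 mg.
- At 50 mg: 3 capsules, 3 × 50 = 150 mg. Still preventable: 0.
- The check comes 5 days after the first capsule and 3 days after the first 50 mg capsule.

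**Case B: first capsule the day after handout.** Handout on Sunday, capsule 1 on Monday, return on Friday before capsule 5.
- Taken by the check: 4 capsules, 25 + 25 + 50 + 50 = 150 mg.
- At 50 mg: 2 capsules, 2 × 50 = 100 mg. Still preventable: 1.
- The check comes 4 days after the first capsule and 2 days after the first 50 mg capsule.

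**A form on dosing day 3, before that day's capsule**
- Taken: 2 capsules, 25 + 25 = 50 mg. At 50 mg: none. Still preventable: 3 capsules, 150 mg.
- Gain over the plan for a reaction not otherwise reported: 3 − 1 = 2 capsules (100 mg) in case B, 3 − 0 = 3 capsules (150 mg) in case A.

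**Order of treatment.** Both weeks follow the same pattern, so the result does not depend on which week holds naltrexone. For the half who take placebo first, the visit 2 questionnaire comes before any naltrexone, so their first dated check on the drug is the one at the end of week 2.

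**Burden of the fix.** 10 participants × 2 weeks = 20 forms; 20 / 12 = 1.7 per month.

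**Cost if a pair is lost.** Two-sided paired t-test, alpha 0.05, d = 1.0, noncentrality d√n, n − 1 degrees of freedom:
- n = 10: noncentrality 3.162, critical t 2.262, power 0.803.
- n = 9: noncentrality 3.000, critical t 2.306, power 0.748.

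Section IV.F states 80% power at d = 1.0 with 9 adults; this calculation gives 75% with 9 and 80% with 10. The difference matters here only for pricing a lost pair.

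**The case against.** The strongest reply is that the protocol never promises a tolerability gate. IV.D.d.iii says the dose is set beforehand, and a fixed low start does useful work by itself, because a first reaction would occur at half the final dose. That stands. A reader might infer that the protocol contradicts itself, but the documents do not support this: the low-dose days serve part of their stated purpose without any check.

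A reader might also infer that a reaction at 25 mg cannot stop the increase. That is too strong. The capsules are taken at home, so a participant who feels unwell can skip one or contact the team. Section IV.D.d.ii lists symptoms that patients should report and says treatment may have to be stopped. The consent and contact pages, where reporting instructions may sit, were removed from the text, so their absence counts for nothing. The questionnaire in IV.D.d.iii is undated. Taking it to be the one at the visits is likely right, but it is an inference. What can be said is that the documents schedule no check in the window.

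Daily contact through the text and video also exists, and reviewing the videos might show that something is wrong. The protocol describes this for adherence only, so it is not a planned safety check.

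Finally, the milligram figures are schedule arithmetic and show no harm. That is correct and limits the weight of the point. It does not remove the point: followed as written, the plan doubles the dose before any dated question about symptoms.

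**Conclusion.** The concern holds in a limited form. The documents place no side-effect check between the second 25 mg capsule and the first 50 mg capsule. The dated checks come after two or three 50 mg capsules (100 or 150 mg at that strength), when at most one remains to be prevented. A reaction at 25 mg that the participant neither volunteers nor acts on would not be found by a dated study procedure before the dose doubles.

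This rests on two assumptions: that the undated questionnaire in IV.D.d.iii is the one given at the visits, and that the first capsule is taken on the day of handout or the day after. The documents give no rate of reactions or of non-reporting, so the number affected is unknown; with about 10 participants it is probably small. The gap bears on safety and does not bias any outcome or analysis. It is a minor safety improvement.

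**What to change.** In IV.C.a and IV.D.d.iii, send the existing side-effect questionnaire through REDCap with the 9 am text on dosing day 3, to be answered before that day's capsule. Do this in both weeks, so that the form does not reveal which week holds naltrexone.

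- None or mild: take the capsule as planned.
- Moderate or severe: hold the capsule until the nurse or physician follow-up that IV.C already describes for the visits. The clinician, still blinded, decides whether to continue or to stop that week's capsules.
- Record every stop.

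Replacement capsule sets, rescheduled scans and withdrawal are best left to the investigator. Fixed rules for these could remove pairs selected on tolerability of the drug, which is a debatable trade in so small a study.

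The cost is about 20 short forms, fewer than two a month, and brief clinician availability on those mornings (Wednesdays if the listed weekdays are kept). Stopping the capsules also gives up the steady state that section II presents as a strength of the design, and may lose a pair: power at d = 1.0 is about 80% with 10 pairs and 75% with 9. Some of these participants might have missed the scan anyway under the existing follow-up.
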